16. WITHDRAWAL OF SUBJECTS

- *Describe anticipated circumstances under which subjects will be withdrawn from the research without their consent*
- *Describe procedures for orderly termination*
- *Describe procedures that will be followed when subjects withdraw from the research, including partial withdrawal from procedures with continued data collection.*

Participants may withdraw voluntarily from the study at any given time with no reason as is outlined in the informed consent for participation in the study. Any participant who withdraws from a study arm will still be contacted for follow-up assessments as outlined within this protocol unless the participant elects to forgo follow-up contact with the study assessors. This will include the surveys for outcome assessment, phone calls made on the subsequent postoperative days and the office visit following surgery.

Discontinuation from the continuous administration of local anesthetic prior to completion of the medications' dosing will not be deemed a withdrawal from the study but rather a discontinuation of treatment and the participant will continue to be followed up with for assessment of study outcomes with notation of the discontinuation of treatment within the database and the reason for discontinuation documented.

All participants who discontinue intervention will be followed in order to assess for potential adverse events, serious adverse events and any unanticipated problems pertaining to the use or administration of the study medications.

Adverse events include but are not limited to block failure, allergy to local anesthetic, persistent pain at injection/catheter site, local skin irritation at catheter site, pump/device failure.

Should a participant experience any of the serious adverse events listed in the next section, this participant will immediately be halted from their study intervention. These patients will be recommended to seek immediate care for assessment of their serious adverse event to best ensure patient safety. Should a patient experience an adverse event or unanticipated event, the study investigator who is contacted will determine if the participant's event meets criteria for discontinuation of treatment.

ADVERSE EFFECTS OF TREATMENT

Risks associated with single shot adductor canal block

1. Peripheral Nerve Injury

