 - i. 1.5 ml kg⁻¹ bolus of 20% lipid emulsion Infusion at 0.25 ml kg⁻¹ per min for at least 10 min after return of circulatory stability Consider giving a second bolus and increasing infusion to 0.50 ml kg⁻¹ if circulatory stability not attained Upper limit of lipid emulsion recommended is 10 ml kg⁻¹ over the first 30 min.
- d. In addition, the patients will be on a monitor in the post anesthesia recovery unit until they are deemed stable and ready for discharge. Any abnormalities will be noted by the nurse taking care of the patient who would inform the anesthesiologist and surgeon. This is standard protocol at our institution when any regional blocks are given for post-operative patients.
- e. The patients will be given a hand out and instructed to watch for signs or symptoms such as chest pain, rapid heart beating, difficulty breathing, or seizure like activity. If any of these symptoms are present, they would normally be observed immediately after the block is performed or while the patient is still being monitored, however after discharge they will still be informed to watch for symptoms in the event of a delayed response. They will be instructed to call the study PI or safety officer and likely be sent to the emergency room for evaluation.

3. Local Infection

- a. For single shot adductor canal blocks the risk of infection is very low. To minimize this risk the site is prepped in sterile fashion with either chlorhexidine or iodine scrub. The injecting physician washes hands and uses sterile gloves and instruments for the course of this procedure.
- b. Perioperative antibiotics will also be given which is standard protocol for ACL reconstruction regardless of catheter insertion or not.
- c. In the event that the patient notices any skin irritation, redness, foul smell, or drainage form the site of the injection, they will be advised to first call the safety officer, PI, or other co-investigator to describe their symptoms. The patients will also watch for fevers or chills. If infection is suspected they will be sent to the emergency room or surgeons office for evaluation and further testing. They may be started on a course of oral antibiotics if an infection is concerning after evaluation.

Risks associated with continuous peripheral nerve catheter placement:

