- Significant study intervention non-compliance

- If any clinical adverse event (AE), laboratory abnormality, or other medical condition or situation occurs such that continued participation in the study would not be in the best interest of the participant. Adverse events or unanticipated events will be assessed on a case by case basis and discontinued as noted in the section above.
- If the participant meets an exclusion criterion (either newly developed or not previously recognized) that precludes further study participation.
- An investigator will discontinue/withdraw a patient from study participation if they are not deemed contactable, this will be defined as inability to contact after 3 separate attempts are made at least 2 hours apart across two days.

The reason for participant discontinuation or withdrawal from the study will be recorded on the Case Report Form (CRF) as noted in the section above. Subjects who sign the informed consent form and are randomized but do not receive the study intervention they are randomized to will be followed in the study as if they have obtained their intervention this deviation from protocol will be documented for post-hoc analysis reasons. Subjects who sign the informed consent form, and are randomized and receive the study intervention, and subsequently withdraw, or are withdrawn or discontinued from the study, maintained in the group to which they are randomized for assessment documentation with notation made as to their withdrawal to assist in the post-hoc analysis.

Study participants who are randomized to the continuous infusion cohort will be provided with information about the pumps themselves and troubleshooting advice. They will also be provided with contact information for the investigators should they run into issues. The troubleshooting of the device will be done as noted in the above section and need for discontinuation of the therapy will be assessed as noted above with safety concerns as the primary reason for discontinuation.

A participant will be considered lost to follow-up if he or she fails to respond to study surveys followed for more than one day of follow up, misses the phone calls, or misses the post-operative office visit planned for postoperative day 10-14 and is unable to be contacted by the study site staff.

The following actions must be taken if a participant fails to respond to study surveys or return to the clinic for a required study visit:

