- a. Localized inflammation is infrequent (0–10%), and local infection (0–3%), abscess formation (0–0.9%), and sepsis occur even more rarely.
- b. Transparent dressings are used to reduce the number of dressing changes while appropriately monitoring the site for signs of inflammation
- c. Since the continuous catheter remains in for 48-72 hours, it does pose a theoretical increased risk of infection compared to a single shot adductor canal block although this has not been proven in the literature. To minimize this risk the site is prepped in sterile fashion with either chlorhexidine or iodine scrub. The injecting physician washes hands and uses sterile gloves and instruments for the course of this procedure.
- d. Perioperative antibiotics will also be given which is standard protocol for ACL reconstruction regardless of catheter insertion or not.
- e. In the event that the patient notices any skin irritation, redness, foul smell, or drainage from the site of the injection, they will be advised to first call the safety officer, PI, or other co-investigator to describe their symptoms. The patients will also watch for fevers or chills. If infection is suspected they will be sent to the emergency room or surgeon's office for evaluation and further testing. They may be started on a course of oral antibiotics if an infection is concerning after evaluation

10. Local Anesthetic System Toxicity

- a. The patients with a continuous catheter will be receiving a fixed rate of flow of local anesthetic to the nerve site for 48-72 hours. This does put them at a theoretical risk for toxicity while they are at home with the catheter in even though the dosage is well below the threshold for systemic toxicity. They will be educated on the following signs and symptoms similar to the single shot patients.
- b. Ranges from mild symptoms of metallic taste, agitation, and circumoral numbness to more severe findings such as seizure, respiratory arrest, cardiac arrhythmias.

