- c. Manifestations of local anesthetic toxicity typically appear 1 to 5 minutes after the injection, but onset may range from 30 seconds to as long as 60 minutes. These symptoms will be monitored for and usually happen because of accidental injection into the vascular system. This is exceedingly rare with the advent of ultrasound guidance and direct visualization of the injection. During the procedure the patients are attached to full monitors which will monitor blood pressure, cardiac rhythm, oxygen saturation. Any noticeable severe findings are treated with supportive care with propofol, lipid infusions which can reverse the effects from the local anesthesia.

d. Lipid infusion protocol as recommended by the ASEA practice advisory on local anesthetic systemic toxicity is as follows:

- i. 1.5 ml kg⁻¹ bolus of 20% lipid emulsion Infusion at 0.25 ml kg⁻¹ per min for at least 10 min after return of circulatory stability Consider giving a second bolus and increasing infusion to 0.50 ml kg⁻¹ if circulatory stability not attained Upper limit of lipid emulsion recommended is 10 ml kg⁻¹ over the first 30 min.
- e. In addition, the patients will be on a monitor in the post anesthesia recovery unit until they are deemed stable and ready for discharge. Any abnormalities will be noted by the nurse taking care of the patient who would inform the anesthesiologist and surgeon. This is standard protocol at our institution when any regional blocks are given for post-operative patients.
- f. The patients will be given a hand out and instructed to watch for signs or symptoms such as chest pain, rapid heart beating, difficulty breathing, or seizure like activity. If any of these symptoms are present, they would normally be observed immediately after the block is performed or while the patient is still being monitored, however after discharge they will still be informed to watch for symptoms in the event of a delayed response. They will be instructed to call the study PI or safety officer and likely be sent to the emergency room for evaluation.

Unanticipated events will be assessed on a case by case basis and the study investigators will determine if the patient should be halted/discontinued and whether or not they should seek immediate care.

Since identifiers are being recorded, there is also risk of loss of confidentiality of the patients

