18. RESEARCH RELATED HARM/INJURY

- *Describe the availability of medical or psychological resources that subjects might need as a result of anticipated problems that may be known to be associated with the research.*
- *If the research is greater than minimal risk, explain any medical treatments that are available if research-related injury occurs, who will provide it, what will be provided, and who will pay for it.*

Adverse events and planned interventions prior to discontinuation

- Failure of catheter placement despite successful administration of single site injection- any participant who was randomized to receive a continuous

pump, but the catheter was unable to be placed will be discontinued from the continuous pump protocol, however these patient's will continue to be followed according to the above stated protocol and their outcomes assessed in an intent-to treat manner based on their initial randomization.

- Continuous Block failure- if patient perceives no benefit from block but pump appears to be functioning patient will be requested to continue the pumps use until the medication dosing is completed, a perceived block failure will be documented.
- Allergy to local anesthetic- if a patient reports a systemic allergic response including but not limited to shortness of breath, diffuse rash, or angioedema the patient will be recommended to discontinue the intervention and seek emergency care. If the patient reports a local confined rash or skin irritation around the catheter site with no systemic symptoms the patient will be recommended to take a dose of Benadryl and apply a warm compress, if symptoms resolve the patient will remain in the study if there is no resolution the patient will be told to discontinue the medication administration and seek care for further evaluation.
- Persistent pain at catheter site- the patient will be advised to place a cold or warm compress at the catheter site and adjust the adhesive bandage if necessary if these interventions do not alleviate the participants pain within 12 hours the patient will be advised to discontinue the intervention.

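### The catheter arm's systemic toxicity item (f) reuses the single-shot instruction and does not carry over the protocol's own rule of immediate halt and immediate care

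*Combined protocol and SAP*

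**What the plan says.** The protocol lists treatment risks twice, in Section 16 (Withdrawal of Subjects, under Adverse Effects of Treatment) and in Section 17 (Risks to Subjects). In each list the last catheter item on local anesthetic systemic toxicity, item (f), covers symptoms at home: chest pain, a racing heart, breathing difficulty or something resembling a seizure. Patients get a handout and are told what to watch for. Then: "They will be instructed to call the study PI or safety officer and likely be sent to the emergency room for evaluation".

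Item (a) of the same list recognises that these patients are in a different position from single-shot patients. It speaks of their "theoretical risk for toxicity while they are at home with the catheter in even though the dosage is well below the threshold for systemic toxicity".

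Other parts of the protocol bear on stopping the infusion:

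- Section 16, before the risk list, covers a participant who has one of the listed serious adverse events: "this participant will immediately be halted from their study intervention. These patients will be recommended to seek immediate care".
- Section 16, on pump problems, says patients receive investigator contact details and that "need for discontinuation of the therapy will be assessed as noted above with safety concerns as the primary reason for discontinuation".
- Section 18, on allergy, covers a patient who reports a systemic response such as "shortness of breath, diffuse rash, or angioedema the patient will be recommended to discontinue the intervention and seek emergency care".
- Section 18, on persistent pain at the catheter site, says that after compresses and bandage adjustment, "if these interventions do not alleviate the participants pain within 12 hours the patient will be advised to discontinue the intervention".
- Section 11 has catheter patients taught pump function, troubleshooting and removal at home before discharge, with written instructions.

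**The concern.** The instruction was written for a single injection. It expects symptoms at the time of the block or during monitoring, and treats anything later as an exception: "however after discharge they will still be informed to watch for symptoms in the event of a delayed response". A single-shot patient has nothing to switch off. A catheter patient has a source of drug still running, and item (f) gives as the first action a call to the study team, with the emergency room as a likely next step.

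The protocol names seizures, arrhythmia and respiratory arrest as the severe forms of this event. If the text is followed as written, the infusion may continue while a call is placed and answered. A patient who is having a seizure cannot make the call at all, and the item says nothing about a companion.

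**Working it through.** No alpha, power or effect size is involved. The check is a comparison of texts, with three small counts.

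1. **Is the wording reused?** I compared four items: single-shot toxicity item (e) in Section 16 (item 2) and Section 17 (item 5), and catheter toxicity item (f) in Section 16 (item 5) and Section 17 (item 10). The symptom list, the remark about delayed onset and the closing instruction are the same in all four. The onset statement is also shared: 30 seconds to 60 minutes after the injection. That describes one dose, not an infusion of 48 to 72 hours.

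2. **Does item (f) say to stop the pump?** No, in either copy. The other catheter toxicity items, (a) to (e), do not say so either, but (b) to (e) deal with symptom range, onset and procedural monitoring, lipid rescue and recovery-room monitoring. A home instruction would not belong there. The gap is therefore one item, printed twice.

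3. **Is there a stop rule elsewhere?** Yes. The Section 16 halt rule can reasonably be read to cover systemic toxicity, because toxicity is in the risk list that follows. Three things are unsettled: the list does not label which risks are serious adverse events, the rule is in the passive and names nobody to stop the pump, and it does not place the stop before or after the call. Item (f) does not refer to it.

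4. **How is a similar symptom handled?** In Section 18, reported shortness of breath as part of a systemic allergic response leads to stopping and seeking emergency care. In item (f), breathing difficulty leads to a call and a probable referral. Both routes may begin with the patient's report; the difference is that one ends in a definite stop and the other does not. A patient at home cannot be expected to tell the two causes apart.

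5. **What does Section 18 cover?** It has five entries: catheter placement failure, block failure, allergy, site pain and pump failure. Block failure continues the infusion, and placement failure has no running pump. Entries that stop a running infusion: 5 − 2 = 3. None of the five is for systemic toxicity.

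6. **Who is exposed, and how often are they called?** With 1:1 allocation of 78, 78 / 2 = 39 catheter patients. Adverse-event calls fall on post-operative days 1, 2, 3, 4 and 7. Counting from the day of surgery, a 48-hour infusion spans two calls (days 1 and 2) and a 72-hour infusion three (days 1 to 3). About one call a day helps detection but does not replace an instruction for acute symptoms.

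**The case against.** The strongest reply is that the protocol already has the rule. Section 16 ties the halt to the participant having the serious event, and it reserves the contacted investigator's judgement for other adverse or unanticipated events. This stands. A reader might infer from item (f) that the protocol has no step to stop the pump, or that the halt applies only once the study team has been reached. The documents support neither: the halt rule exists and is not worded as conditional on contact. Nor does item (f) leave out emergency care; it makes it likely rather than definite.

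A second reply concerns Section 18. Its list is headed as interventions to try before discontinuation, so the absence of a toxicity entry is largely explained by its purpose. That also stands, and I do not rest the point on that absence. The allergy entry remains a fair comparison because the symptoms overlap.

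Third, the handout and written pump instructions, which the patient would actually use, are not in the documents and may contain the step. This limits the point to the protocol text. It does not remove it, because the text states an order of actions that fits poorly with the halt rule.

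Fourth, the risk is described as theoretical at a dose well below the toxic threshold. That is accepted. The argument rests on the severity of the named events and the small cost of the change, not on frequency.

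**Conclusion.** The point holds as a correction to safety wording. Item (f) for the catheter arm takes over a single-injection instruction, puts a call to the study team first, and does not carry over the immediate-halt and immediate-care rule that Section 16 sets for listed serious events. That rule in turn leaves open who stops the pump and when.

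Its size is one item in two places, relevant to 39 planned patients for 48 to 72 hours each. No rate of toxicity during infusion is given, so no expected number of events can be stated. No endpoint, analysis or sample size changes. The conclusion assumes that toxicity falls under the halt rule, as its place in the risk list suggests. It makes no claim about what the handout says. I would class it as a cheap improvement worth making.

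**What to change.** In both copies of catheter item (f), state that a patient at home with any of the listed symptoms, or a person with them, stops or disconnects the pump as taught, seeks emergency care at once, and then notifies the study team. Add a cross-reference to the Section 16 halt rule, and in that rule say who stops the pump and that this comes before the call. Check that the handout and the pump-use and removal instructions agree; if they already do, only the protocol text needs aligning.

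The cost is wording. Home pump removal is already taught, so no extra visits, staff or patients are needed. The downside is an occasional unnecessary pump stop or emergency visit. Follow-up is not lost, because under Section 16 an infusion ended early "will not be deemed a withdrawal from the study but rather a discontinuation of treatment", and outcome assessment continues.

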18. RESEARCH RELATED HARM/INJURY

- *Describe the availability of medical or psychological resources that subjects might need as a result of anticipated problems that may be known to be associated with the research.*
- *If the research is greater than minimal risk, explain any medical treatments that are available if research-related injury occurs, who will provide it, what will be provided, and who will pay for it.*

Adverse events and planned interventions prior to discontinuation

- Failure of catheter placement despite successful administration of single site injection- any participant who was randomized to receive a continuous

pump, but the catheter was unable to be placed will be discontinued from the continuous pump protocol, however these patient's will continue to be followed according to the above stated protocol and their outcomes assessed in an intent-to treat manner based on their initial randomization.

- Continuous Block failure- if patient perceives no benefit from block but pump appears to be functioning patient will be requested to continue the pumps use until the medication dosing is completed, a perceived block failure will be documented.
- Allergy to local anesthetic- if a patient reports a systemic allergic response including but not limited to shortness of breath, diffuse rash, or angioedema the patient will be recommended to discontinue the intervention and seek emergency care. If the patient reports a local confined rash or skin irritation around the catheter site with no systemic symptoms the patient will be recommended to take a dose of Benadryl and apply a warm compress, if symptoms resolve the patient will remain in the study if there is no resolution the patient will be told to discontinue the medication administration and seek care for further evaluation.
- Persistent pain at catheter site- the patient will be advised to place a cold or warm compress at the catheter site and adjust the adhesive bandage if necessary if these interventions do not alleviate the participants pain within 12 hours the patient will be advised to discontinue the intervention.

Pump/device failure- if the participant reports that the pump does not appear to be functioning properly the investigator who was contacted will assist the participant with troubleshooting the pump over the phone. If the investigator deems that the pump does not appear to be functioning after two independent attempts at troubleshooting/restarting the participant will be advised to discontinue the intervention at that time.

